7.7. Concomitant Therapy

Table JZDA.7.5 describes medications, treatments, and drug classes that are restricted or prohibited for use during the study treatment period, including exceptions and conditions. There are no prohibited therapies during the postdiscontinuation follow-up period. Patients who, in the opinion of the investigator, require the use of any of the prohibited treatments for clinical management should be discontinued from the trial. Patients may receive other supportive therapy that the investigator deems to be medically necessary.

In general, medications or live vaccinations specifically prohibited in the exclusion criteria are not allowed during the ongoing trial.

Table JZDA.7.5. Concomitant Medication Guidelines

Therapy	As Needed	Chronic Use	Exceptions or Conditions for Use
Antiplatelet therapy	Yes	Yes, with restrictions	Chronic use of aspirin up to 325 mg/day is permitted
Anticoagulation therapy	No	Yes, with restrictions	Patients who are on full-dose anticoagulation must be on a stable dose (minimum duration 14 days) of oral anticoagulant or low-molecular-weight heparin or similar agent. If on warfarin, the patient must have an INR of ≤ 3 and no active bleeding or pathological condition present that carries a high risk of bleeding (for example, tumor involving major vessels or known varices).
Colony-stimulating factors	Yes	No	Follow local guidelines. No prophylactic use
Erythroid growth factors	Yes	No	Follow local guidelines
Experimental medicines or investigational agents	No	No	

Concomitant Medication Guidelines

Therapy	As Needed	Chronic Use	Exceptions or Conditions for Use
Glucocorticoids	Yes, with restrictions	Yes, with restrictions	
Use of corticosteroids for the management of investigational product-related AEs or in patients with contrast allergies is acceptable. A temporary course of corticosteroids will be allowed for other indications, at the discretion of the principal investigator (for example, chronic obstructive pulmonary disease, radiation, nausea). Systemic corticosteroids doses should not exceed 10 mg/day of prednisone or equivalent (except as stated otherwise in this protocol).
 
The use of physiologic doses of corticosteroids may be approved after consultation with Lilly.
 
The use of topical, ophthalmic, inhaled, and intranasal corticosteroids is permitted.

Immunosuppressive medications other than glucocorticoids (including, but not limited to methotrexate, azathioprine, and TNF- α blockers)	No	No	Use of immunosuppressive medications for the management of AEs related to LY3415244 or in patients with contrast allergies is acceptable
NSAIDs	Yes	No	
See guidance for aspirin on the “antiplatelet therapy” line above.
 
Chronic use of other NSAIDs is not permitted.
 
However, in certain medical situations, NSAIDs may be the best treatment option (for example, for pain management) and are therefore permissible as needed.

Abbreviations: AE = adverse event; INR = international normalized ratio; NSAIDs = nonsteroidal

anti-inflammatory drugs; TNF = tumor necrosis factor.

No other chemotherapy, systemic radiotherapy, immunotherapy, cancer-related hormone therapy, experimental drugs, or herbal supplements intended to treat cancer will be permitted while the patients are on this study.

Palliative radiation therapy to small areas of painful metastases that cannot be adequately managed with systemic or local analgesics is permitted after discussion with and agreement of the Lilly CRP/CRS.

In addition, any disease progression requiring other forms of specific antitumor therapy will also necessitate early discontinuation from the study. Appropriate documentation for all forms of premedication, supportive care, and concomitant medications must be captured on the eCRF. Replacement hormonal therapy initiated before study entry will be allowed.

Patients should receive full supportive care. The use of granulocyte-colony stimulating factor (G-CSF) is permitted at the discretion of the investigator based on American Society of Clinical

Oncology (ASCO) (Smith et al. 2015) and European Society for Medical Oncology (Crawford et al. 2010) guidelines.

If clinically indicated at any time during the study, erythropoietin and packed red blood cell transfusions may be used according to ASCO guidelines (Rizzo et al. 2008). Prophylactic antibiotic treatment should be consistent with ASCO guidelines (Flowers et al. 2013).

All concomitant medications should be recorded throughout the patient's participation in the study.

7.8. Treatment after Study Completion

7.8.1. Continued Access

[figure not shown]
Patients who are still on study drug at the time of study completion may continue to receive study drug if they are experiencing clinical benefit and no undue risks.

The continued access period will apply to this study only if at least 1 patient is still on study drug when study completion occurs. Lilly will notify investigators when the continued access period begins.

Lilly may allow patients to enroll in a “rollover” protocol to provide long-term continued access for patients enrolled in this study.

Patients who are in short-term follow-up when the continued access period begins will continue in short-term follow-up until the 90-day short-term follow-up visit is completed. Long-term follow-up does not apply.

Patients who are in long-term follow-up when the continued access period begins will be discontinued from long-term follow-up.

^a Lilly will notify sites when the continued access period begins and ends.

^b Final analysis of overall survival. Lilly will notify sites when study completion occurs.

^c End of study occurs at the last visit or last scheduled procedure for the last patient.

Figure JZDA.7.1. Continued access diagram.

8. Discontinuation Criteria

The reasons for treatment and study discontinuation and the dates of discontinuation will be collected for all patients.

Patients who discontinue during the study treatment period, whether or not they received study treatment, will have follow-up procedures performed as shown in the Schedule of Activities (Section 2).

If a patient withdraws informed consent, he or she must not be contacted unless he or she has explicitly provided permission and consent. Lilly may continue to use previously collected medical research data prior to the withdrawal consistent with the original authorization.

8.1. Discontinuation from Study Treatment

Patients will be discontinued from study treatment in the following circumstances:

- the patient is enrolled in any other clinical study involving an investigational product or any other type of medical research judged not to be scientifically or medically compatible with this study.
- the patient becomes pregnant during the study
- the patient is significantly noncompliant with study procedures and/or treatment as described in Section 7.6
- The patient experiences a DLT (see Section 7.2.2.2) during Cycle 1, a DLT-equivalent toxicity (see Section 7.2.2.2.2), or other unacceptable toxicity
- the patient requires a dose delay of >28 days, except as described in Section 7.4
- the patient, for any reason, requires treatment with another therapeutic agent that has been demonstrated to be effective for treatment of the study indication.
Discontinuation from study treatment will occur prior to introduction of the new agent
- the investigator decides that the patient should be discontinued from study treatment
- the patient requests to be discontinued from study treatment
- the patient has received the maximum duration of 12 months of study treatment (longer duration may be considered for a patient receiving clinical benefit, in consultation with the Lilly CRP/CRS). If tumor imaging shows initial disease progression, at the discretion of treating physician, patients may remain on study treatment with repeat imaging 4 to 6 weeks later to assess tumor response or confirm progression per RECIST 1.1 with confirmatory scan on disease progression

Patients who are discontinued from study treatment will have follow-up procedures performed as shown in the Schedule of Activities (Section 2).

Discontinuation of study treatment may be considered for patients who meet all of the following criteria:

- have a confirmed CR, **and**
- have received study treatment for at least 24 weeks, **and**
- have received at least 2 cycles of study treatment beyond the date when the initial CR was declared.

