7.2.2.2. Dose-Limiting Toxicity Determination

A DLT is defined as any of the events listed in [Table JZDA](#), if the event occurs during the DLT observation period (Cycle 1) in Phase 1a, and toxicity that is not clearly and directly related to the primary disease or another etiology.

All AEs of Grade 3 or higher that occur during the DLT observation period will be included in the DLT definition except for toxicities with a clear, alternative explanation, including the exceptions listed in Section [7.2.2.2.1](#).

Patients who experience a DLT in Cycle 1 will be discontinued from study treatment.

Table JZDA.7.2. Dose-Limiting Toxicity

Hematologic toxicity

 Grade 3 thrombocytopenia requiring platelet transfusion or Grade 4 thrombocytopenia of any duration Grade ≥ 3 febrile neutropenia Grade ≥ 3 anemia requiring a blood transfusion Other Grade 4 toxicity lasting >7 days, excluding toxicities listed in Section 7.2.2.1
Nonhematologic toxicity – nonlaboratory

 Grade 4 irAE, except as stated otherwise below Grade ≥ 3 colitis or noninfectious pneumonitis Other Grade 3 irAE, excluding colitis or pneumonitis, that: 
 does not downgrade to Grade 2 within 3 days after onset of the event despite optimal medical management including corticosteroid therapy, or does not downgrade to Grade ≤ 1 or the patient's baseline level within 14 days after onset of the event Grade 2 pneumonitis that does not resolve to Grade ≤ 1 within 3 days after initiation of optimal medical management including corticosteroids therapy Grade ≥ 3 toxicity lasting an extended period of time despite optimal supportive care (for example, nausea, vomiting, and diarrhea lasting >3 days) Grade ≥ 3 fatigue lasting >7 days Grade ≥ 3 hypertension despite of maximal medical therapy
Nonhematologic toxicity – laboratory/investigations

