7.2.2.2. DLT-Equivalent Toxicities

A DLT-equivalent toxicity is any event listed in [Table JZDA.7.2](#) occurring after Cycle 1 in Phase 1a or in any cycle of Phase 1b that would have met criteria for DLT if it had occurred during the DLT observation period. For individual patients experiencing a DLT-equivalent toxicity, dose modifications will be made as outlined in Section [7.4](#).

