7.4. Dose Modification

No dose modification is allowed during Phase 1a DLT observation period (Cycle 1).

After the Phase 1a DLT observation period (Cycle 1), doses of the study drug may be delayed or discontinued to manage specific AEs or other toxicities. Dose reductions are not permitted. All dose modifications should be documented, including the approach taken and a clear rationale for the need for modification.

The investigator must assess whether the toxicity is at least possibly due to study treatment and apply the dose-modification guidelines. Investigators are encouraged to consult Lilly for additional guidance.

If a patient requires a dose delay, study treatment should be resumed within 1 cycle, if possible and appropriate. If study treatment cannot be resumed within 1 cycle, every effort should be made to restart on the first day of the next cycle. In rare circumstances, a delay of >28 days may be permitted before permanent treatment discontinuation, as long as the patient demonstrates clinical benefit, does not have objective progression, and is recovering from the toxicity. Such circumstances must be discussed with the Lilly CRP/CRS.

Adverse events of immune-related etiology are expected because of the study drug's mechanism of action and may occur shortly after the first dose or several months after the last dose. Study treatment must be withheld if the patient experiences a drug-related toxicity or a severe or life-threatening AE. Dose reductions are not permitted.

A 4-hour observation period is required after the administration of LY3415244 in Cycles 1 to 3. During observation period, patients treated with LY3415244 should be closely monitored for signs and symptoms indicative of an infusion-related reaction by medical staff from the start of the infusion until 4 hours after the end of the infusion, in an area where emergency medical resuscitation equipment and other agents (epinephrine prednisolone equivalents, etc.) are available. LY3415244 infusion-related reactions will be defined according to the Common Terminology Criteria for Adverse Events (CTCAE), Version 4.0 definition of IRRs.

Table JZDA.7.3 presents instructions for management of infusion-related reactions associated with LY3415244.

Table JZDA.7.3. Management of Infusion-Related Reactions

Grade	Management
2	First occurrence

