Other corticosteroid options can be given at equivalent doses. Corticosteroids should be tapered over 1 month once symptoms improve to Grade \leq 1, and study treatment should not be restarted until corticosteroid tapering is complete. During corticosteroid use, use prophylactic antibiotics to prevent opportunistic infections.

Table JZDA.7.4. Dose Modification Guidelines and AE Management for Toxicities At Least Possibly Related to Study Drug

SOC	Toxicity	CTCAE Grade and/or Symptoms ^a		Treatment Plan ^b
		Grade	Symptoms	
Endocrine	Thyroid issues		If symptomatic	
 Start thyroid replacement therapy and/or medical management and continue study treatment For Grade 3 hyperthyroidism, withhold study treatment until hyperthyroidism improves to Grade ≤ 1 For Grade 4 hyperthyroidism, discontinue study treatment
Endocrine	Hypotension, altered mental status, headache, fatigue, hyperglycemia		For endocrine issues other than thyroid issues (for example, hypophysitis, diabetes mellitus-type 1)	
 Withhold study treatment and administer prednisone 1-2 mg/kg/day Resume study treatment when symptoms resolve and the patient is stable on hormone replacement therapy For Grade 3 or 4, discontinue study treatment For severe adrenal crisis, give stress dose of IV corticosteroids with mineralocorticosteroid

Dose Modification Guidelines and AE Management for Toxicities At Least Possibly Related to Study Drug

SOC	Toxicity	CTCAE Grade and/or Symptoms ^a		Treatment Plan ^b
		Grade	Symptoms	
Gastrointestinal	Diarrhea, Abdominal pain, Blood in stool, Colitis	2		
 Withhold study treatment, give antidiarrheal medication, and check etiology If the event continues for >5 days despite the use of antidiarrheal medications, start prednisone 0.5-1 mg/kg/day Resume study treatment after the event resolves to Grade ≤ 1
	Diarrhea, Ileus, Perforation, Colitis	≥ 3		
 Withhold study treatment and administer prednisone 1-2 mg/kg/day (no corticosteroids if possible perforation) If the event persists >3 days despite use of corticosteroids, add a nonsteroidal immunosuppressive agent and discontinue study treatment.^c Resume study treatment after the event resolves to Grade ≤ 1 Discontinue study treatment if Grade 3 persists For Grade 4, discontinue study treatment

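### Section 8.1 makes every DLT-equivalent toxicity a permanent stop, but Table JZDA.7.4 lets Grade 3 colitis that settles promptly resume at full dose, and no text says which rule governs

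*Protocol*

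**What the plan says.** Protocol Section 8.1 is a mandatory list. One entry reads "The patient experiences a DLT (see Section 7.2.2.2) during Cycle 1, a DLT-equivalent toxicity (see Section 7.2.2.2.2), or other unacceptable toxicity". It carries no exception. The next entry, on long dose delays, does carry an exception that points to Section 7.4.

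Section 7.2.2.2.2 (DLT-Equivalent Toxicities; the heading in the body prints as 7.2.2.2) defines such a toxicity as a Table JZDA.7.2 event occurring after Cycle 1 of Phase 1a or in any cycle of Phase 1b. It then says: "For individual patients experiencing a DLT-equivalent toxicity, dose modifications will be made as outlined in Section" 7.4. Section 7.4 says that after Cycle 1 "doses of the study drug may be delayed or discontinued to manage specific AEs or other toxicities", and it rules out dose reduction.

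The two tables say the following.

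- Table JZDA.7.2 lists "colitis or noninfectious pneumonitis" at Grade 3 or higher, with no minimum duration. It also lists "Grade 2 pneumonitis that does not resolve to Grade" 1 or less within 3 days of starting optimal management, and ALT or AST >3x ULN with bilirubin >2x ULN without cholestasis.
- Table JZDA.7.4 is titled "Dose Modification Guidelines and AE Management for Toxicities At Least Possibly Related to Study Drug". Its gastrointestinal row for Grade 3 or higher names "Diarrhea, Ileus, Perforation, Colitis" and includes the instruction "Resume study treatment after the event resolves to Grade" 1 or less. The Grade 2 respiratory and Grade 2 hepatobiliary rows also allow resumption once the event is back to Grade 1 or less. Footnote b makes any discontinuation permanent.

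**The concern.** The protocol gives two answers for the same patient. Take a Phase 1b patient with Grade 3 colitis that responds to prednisone within 3 days and returns to Grade 1 or less. Under Section 8.1 the patient is off drug for good. Under Section 7.2.2.2.2 and Table JZDA.7.4 the patient restarts at the full dose once the steroid taper is complete. Two sites could each defend their action from the text.

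The first stake is safety, since the question is whether a patient is re-exposed after a severe immune-related event. The second is reporting. The choice decides whether the patient counts under discontinuations due to AEs (SAP Section 5.12.3) or under dose delays (Protocol Section 10.3.3.4; SAP Section 5.12.1). It also moves dose intensity. SAP Section 5.12.1 ends the exposure denominator 14 days after the last dose, so a stopped patient's denominator excludes the time after the event, while a resumed patient's includes the whole hold.

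**Working it through.** The plan states no figure to reproduce. The check sets the two tables against Section 8.1, event by event, for events after Cycle 1 of Phase 1a or in any Phase 1b cycle.

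**Step 1: scope.** Cycle 1 DLTs are not in conflict, because Section 7.2.2.2 and Section 8.1 both stop treatment. The question concerns only DLT-equivalent toxicities, for which Section 7.2.2.2.2 points to Section 7.4 instead.

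**Step 2: hepatic band.**
- Table JZDA.7.2 event: ALT/AST >3x ULN and bilirubin >2x ULN, without cholestasis.
- Table JZDA.7.4 Grade 2 row: ALT/AST 3x to 5x, or bilirubin 1.5x to 3x. The stop row begins at ALT/AST >5x or bilirubin >3x.
- Part of the Table JZDA.7.2 event not reached by the stop row: ALT/AST >3x to 5x together with bilirubin >2x to 3x.

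**Step 3: compare.**

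| Event | In Table 7.2? | Table 7.4 | Section 8.1 |
|---|---|---|---|
| Grade 3 colitis, prompt return to Grade 1 or less | Yes, any duration | Withhold, prednisone, resume | Stop |
| Grade 2 pneumonitis, not at Grade 1 or less by 3 days | Yes | Withhold, prednisone, resume; no time limit | Stop |
| ALT/AST >3x to 5x with bilirubin >2x to 3x, no cholestasis | Yes | Withhold, prednisone, resume | Stop |
| Grade 4 colitis; Grade 3 or higher pneumonitis; ALT/AST >8x without HCC or liver metastasis | Yes | Stop | Stop |

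**Step 4: does letting Section 8 control remove the conflict?** Under that reading, Table JZDA.7.4 governs only events that fall short of Table JZDA.7.2.
- Pneumonitis: yes. The Grade 2 resume line still serves events that resolve within 3 days.
- Hepatic: yes. The Grade 2 row joins its two criteria with an or, so it still serves an isolated transaminase or isolated bilirubin rise.
- Colitis: no. Table JZDA.7.4 covers toxicities judged at least possibly due to the drug. A Grade 3 colitis of that kind is not clearly due to the disease or another cause, so it meets the DLT definition. Table JZDA.7.2 gives other Grade 3 immune-related events time to improve but excludes colitis from that allowance, and Section 7.2.2.2.1 does not exempt it. The resume line would therefore never apply to colitis, although its row names colitis.

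**The case against.** The strongest defence is that the sections are layered and do not compete. Section 7.2.1 allows dosing to continue until a Section 8 reason is met, which makes Section 8 the outer limit. Table JZDA.7.4 is titled as guidelines, and Section 7.4 lets local standards supersede it where the investigator sees fit. A mandatory criterion ordinarily outranks guidance that can be set aside. Dose modification in this protocol also includes discontinuation, so the reference to Section 7.4 is not in itself a permission to resume.

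Most of this stands. It reconciles the pneumonitis and hepatic events without emptying any resume line, so a reader who counts three irreconcilable conflicts goes further than the text supports.

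Two things remain. Section 7.2.1 does not mention Table JZDA.7.4, and no sentence states the precedence. Colitis also resists the layered reading. The resume line in that row keeps some use, for example for Grade 3 diarrhea lasting 3 days or less, but it has none for the colitis it names. Section 7.4 encourages sites to consult the sponsor on dose modification, which lowers the practical risk but does not settle the rule.

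**Conclusion.** The inconsistency is in the current protocol text. One event, Grade 3 colitis that resolves promptly, is in conflict even if Section 8 is taken to control. Two others, slow Grade 2 pneumonitis and the combined ALT/AST and bilirubin band, are consistent only if Section 8 overrides Table JZDA.7.4, which is implied and not written. The documents give no event rates, so the number of patients affected cannot be computed. The conclusion rests on the wording alone and needs no numerical assumption.

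Three wider inferences are not supported.
- A reader might think dose finding is compromised. The mTPI-2 rules count Cycle 1 DLTs, and the Phase 1b pause (7 or more events in the first 20 patients) counts DLT-equivalent events as they occur, so the colitis is counted whichever way the patient is then handled.
- A reader might blame this wording for the hepatic band with ALT below 5x ULN falling under the combined ALT and bilirubin triggers in Sections 9.4.2 and 9.4.2.1. Those thresholds are a separate choice, and chemistry is scheduled with every infusion and reviewed before dosing.
- A reader might extend the list to Grade 3 creatinine elevation or symptomatic Grade 3 hyperthyroidism. Those depend on how Table JZDA.7.2 is interpreted and are not needed here.

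The point is worth fixing because it concerns a safety stopping rule and the remedy is short.

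**What to change.** State the precedence in one sentence and deal with colitis by name. Either version works, and the clinical choice is the sponsor's.

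- If a mandatory stop is intended: add to Table JZDA.7.4 that its resume instructions do not apply to events meeting Table JZDA.7.2, and take colitis out of the Grade 3 resume line.
- If resumption after resolved Grade 3 colitis is intended: change the Section 8.1 entry to *a DLT-equivalent toxicity, except Grade 3 colitis for which Table JZDA.7.4 permits resumption*. The mandatory stop then stays in place for the pneumonitis and combined ALT/bilirubin events.

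The cost is a short protocol amendment. It touches a safety rule, so it needs ethics review and, where applicable, regulator review, but it can travel with the next amendment. It adds no patients, visits or procedures.

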8.1.1. Discontinuation of Inadvertently Enrolled Patients

If Lilly or the investigator site identifies a patient who did not meet enrollment criteria and who was inadvertently enrolled, a discussion must occur between Lilly CRP/CRS and the investigator to determine if the patient may continue in the study. If both agree that it is medically appropriate to continue, the investigator must obtain documented approval from Lilly CRP/CRS to allow the inadvertently enrolled patient to continue in the study with or without study treatment. Safety follow-up is as outlined in the Schedule of Activities (Section 2).

